In critically ill patients, e.g. in newborns following open heart surgery, it is common for DO_2 to be marginal. This is evidenced by increases in serum markers of anaerobic metabolism (namely serum lactate measurements), by evidence of a high oxygen extraction ratio (low superior vena cava oxyhemoglobin saturations relative to arterial saturations), and by evidence that the cardiovascular system is compensating for inadequate cardiac output (e.g. physical signs of increased systemic vascular resistance and a fast heart rate). When the myocardium receives an insufficient amount of oxygen, tissue hypoxia ensues and causes myocardial dysfunction. Intensive care efforts often focus upon improving tissue perfusion by increasing cardiac output, and this requisitely increases myocardial oxygen demands.² In the most

critically ill patients, the myocardium reaches a profound state of tissue hypoxia which may cause a postoperative loss of circulation (PLOC).

HLHS and the risk of PLOC

Patients with hypoplastic left heart syndrome (HLHS) necessarily have so-called 'single ventricle physiology'. In these patients, the right ventricle pumps blood to both the systemic circulation (to deliver oxygen) and to the lungs (to pick up oxygen, **Figure 2**). Normally, these two functions occur in series, i.e. the right ventricle pumps blood to the lungs and the left ventricle to the body. In two ventricle physiology, each ventricle pumps one cardiac output. In single ventricle physiology, however, the right ventricle pumps to both circulations in parallel, requiring at least 1.6-1.8 cardiac outputs (at times 2-3 cardiac outputs),³ which among other things causes a disproportionate increase in myocardial VO_2 . In the postoperative period, the oxygen extraction capacity of myocardium may be compromised by tissue edema, systemic inflammation, and mitochondrial dysfunction following the effects of cardiopulmonary bypass. Myocardial oxygen delivery can be compromised by anemia (as a consequence of postoperative bleeding), and by inadequate coronary blood flow (especially pronounced in settings of tachycardia - which decreases coronary filling time - and of diastolic hypotension due to the presence of a systemic to pulmonary shunt).

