Typically, SVC saturations are measured by intermittent sampling of blood from a catheter placed into the SVC via the internal jugular vein, or retrograde through the right atrium. The SVC saturation is used to calculate the oxygen extraction ratio, and generally values below 40-50% represent a compromised DO_2 . The limitations to this technique include the following. (1) Blood must be removed from the body (including 'waste' blood which fills the catheter) which can lead to anemia. (2) Even frequent sampling of SVC blood is intermittent, and assessing responses of DO_2 to interventions can be difficult in real time. (3) Frequent entry into the central line can increase the risk of catheter related bloodstream infection. (4) In patients with profoundly low SVC saturations, small amounts of air which enter the blood gas syringe can lead to artificially higher oximetric readings.

To address these limitations, we will test a recently developed central venous catheter which utilizes in vivo reflection spectrophotometry on 4 wavelengths (PediaSat catheter; Edwards Lifesciences) to accurately quantify oxyhemoglobin saturations in blood passing the catheter tip. This catheter is placed in standard fashion, and is coated with both Heparin and antimicrobials in order to diminish the risks of thrombus formation and infection, respectively. Its insertion is similar to standard catheters which are routinely placed in the patient populations being studied here. We have chosen to utilize this catheter in this study because it addresses the pitfalls of our current standard of care above, and because it will allow a continuous, real-time assessment of cardiac output and an estimation of the ratio of pulmonary to systemic blood flow (Q_p/Q_s). Of note, the catheter was recently used to safely and accurately quantify SvO_2 in neonates following cardiac surgery.¹⁰

Serum lactate measurement

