exhibited a pronounced decrease in their measured VO_2 , a pattern which was not present in treated animals which did not experience subsequent hemodynamic instability (**Figure 3**). Having seen this pattern consistently in approximately $n=40$ animal experiments (weight range 2.5-4 kg), we hypothesize that in critically ill patients, VO_2 may decrease below the critical DO_2 and exhibit measureable, even striking, decreases prior to hemodynamic decompensation takes place. If this hypothesis is true, quantification of VO_2 may represent a new 'vital sign' which represents end organ oxygen delivery in critically ill patients. Identification of patients with pathologically supply dependent VO_2 may permit definitive interventions to take place, e.g. initiation of extracorporeal life support, prior to a life-threatening PLOC.

Study Objectives

Specific Aim 1. To demonstrate that oxygen consumption (VO_2) and superior vena cava (SVC) saturations can be safely and precisely measured continuously in newborns undergoing surgery for hypoplastic left heart syndrome (HLHS) or d-transposition of the great arteries with an intact ventricular septum (d-TGA/IVS).

Hypothesis: Measurement of these oxygen-based parameters will not be associated with an increased incidence of equipment-related adverse events (e.g. line displacements, inadvertent extubations) and will lead to precise and reproducible measurements of these important parameters.

Specific Aim 2. To determine whether postoperative loss of circulation (PLOC, defined as cardiac arrest requiring CPR, ECMO cannulation, or causing death) in these patients are associated with a change in oxygen consumption or SVC saturation prior to the event.

Hypothesis: PLOC will be associated with significant decreases in both oxygen consumption and SVC saturations for at least 10 minutes prior to the onset of cardiac arrest.

Specific Aim 3. To determine whether the addition of the oxygen-based measurements to standardly measured parameters (i.e. vital signs, near-infrared spectroscopy

[figure not shown]

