Figure 3. In a proof of concept study, VO_2 monitoring of rabbits (weight ~3 kg) undergoing a 30 minute period of observation, followed by a 15 minute period of asphyxia, then a post-asphyxial recovery. Exemplary VO_2 tracings shown of animals treated (blue line) and untreated (red line) with an intravenous formulation of oxygen which prevented severe hypoxemic-ischemic injury. Animals which suffered severe injury exhibited a significant decrement in VO_2 early during the recovery period, a pattern which worsened prior to post-asphyxial loss of circulation. Animals who experienced treated asphyxial injury had an unchanged VO_2 curve. **A central hypothesis of this study is therefore whether VO_2 may represent a sensitive, real-time, prospective, and non-invasive marker of circulatory failure and inadequate DO_2 in newborns at risk for this life-threatening problem.**

measurements, intermittent measurements of lactate and superior vena cava saturations) add power in predicting which patients will experience PLOC.

Hypothesis: Continuous measurements of VO₂ and SVC saturations will add significantly to our ability to predict which patients will undergo PLOC.

Study Design

We will prospectively and continuously measure VO₂ and SVC saturations in newborns undergoing stage I palliation (S1P) or hybrid palliation (HP) for HLHS (n=20) or arterial switch operation (ASO) for d-TGA/IVS (n=20), beginning at the time of first preoperative intubation and ending at the time of the first postoperative extubation. Newborns will be followed for the occurrence of PLOC as the primary endpoint. A study schematic is attached as **Appendix 1**.

Study Population

Inclusion criteria.

1. Patient from birth to 6 months of age
2. HLHS AND no prior operations AND planned S1P or HP
OR
d-TGA/IVS AND planned ASO
3. Written parental informed consent

Exclusion criteria.

1. Weight < 2 kg
2. Disease specific
 - A. HLHS patients: Infants whose surgical plan includes a neonatal biventricular repair will be excluded.
 - B. d-TGA/IVS patients: Newborns with any additional cardiac defect other than an atrial septal defect will be excluded.
3. Patients on ECMO preoperatively
4. Clinically significant tracheo-esophageal fistula or known preoperative air leak

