 - Oxygen consumption (Q1 second). The VO_2 will be recorded Q1 second as part of the ventilatory parameters described below.
 - SVC saturations (Q1 second). SVC saturations as determined by oximetry will be recorded Q1 second.
- Standard of care monitoring
 - Vital signs. These data will include heart rate, arterial blood pressures, respiratory rate, pulse oximetry, atrial pressures, and central venous pressure. As discussed in detail below, these data will be extracted from an existing program which records the primary data Q5 second in time stamped fashion (T3 Program, Arcardia Solutions).
 - *NIRS*. The near-infrared spectroscopy value represents the oxyhemoglobin saturation of the deep tissues. This will be recorded Q1 second in time-stamped fashion.
 - *Ventilatory parameters*. All ventilation parameters will be recorded from the spirometry recordings from the capnograph. These data include end-tidal CO_2 , fraction of inspired CO_2 , respiratory rate, fraction of inspired O_2 , fraction of expired O_2 , peak end expiratory pressure, peak inspiratory pressure, plateau pressure, mean airway pressure, airway resistance, inspiratory-expiratory time ratio, inspiratory and expiratory times, inspiratory and expiratory tidal volume, compliance of the respiratory system, minute ventilation, VCO_2 , energy expenditure, and respiratory quotient. These data will be recorded Q1 second in time-stamped fashion.
- *Standard labs* will be drawn at the treating team's discretion and gathered from the medical record each day.
 - Arterial blood gas and time drawn
 - Serum lactate and time drawn
 - SVC (or other venous) saturations and time drawn
 - Chemistry profile, complete blood count (white blood cell count, hemoglobin, hematocrit and platelet count), coagulation profile and times drawn
- Treatments
 - *Inotrope infusions* are routinely administered, often in high doses, to these patients in the perioperative setting. It is thought that these infusions affect both oxygen delivery to all tissues, as well as increasing myocardial oxygen consumption.
 - Additionally, we will record *intermittently administered medications*, such as epinephrine, calcium gluconate, sodium bicarbonate, hydrocortisone, and

- thyroid replacement therapy, all of which may affect oxygen consumption and oxygen delivery as well.

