- *Earlier recognition of circulatory failure.* Regardless of a patient's underlying anatomy, the difference in oxyhemoglobin saturation between a patient's systemic arterial and venous circulations represents the adequacy of end organ oxygen delivery (reference Figure 1 above). It is possible that by continuously monitoring both the systemic arterial and venous oxyhemoglobin saturations (the former by pulse oximetry), that the treating team will be able to more rapidly identify evolving circulatory failure. There are many interventions which could be utilized

by the care team prior to PLOC which may improve patient outcomes as a result of and in response to this single factor.

Potential Indirect Benefits

This study has the potential to significantly improve the way that newborn patients (and others) are monitored in the postoperative period. Currently, the circulation of these patients are assessed indirectly, using surrogate measures (using cNIRS, and intermittent lactate and SVC saturations measurements) and vital signs. Because our definitive treatment for refractory circulatory failure is ECMO, and because ECMO itself can cause life-threatening complications, it is extremely challenging to determine which patients are at a higher risk of death or organ injury from inadequate DO_2 compared to the risks of these complications from ECMO. It is possible that if the primary hypothesis of the study, that critically ill patients in the CICU exhibit pathologically supply dependent oxygen consumption, that VO_2 monitoring could add significant, continuous, noninvasive information to the care of newborns during their highest risk period. For the short term, this could permit treating teams to measure the effects of their interventions on oxygen delivery (e.g. addition of inotropes, blood transfusions, clips on shunts) and inform these decisions. For the long-term, it is possible that VO_2 and continuous SVC saturation monitoring could inform a predictive algorithm for the sensitive and specific prediction of which patients suffer from recalcitrant circulatory insufficiency, those which may be at risk for PLOC, and who would benefit from ECMO support. If true, this would likely significantly improve the survival rate and neurologic outcomes of newborns with congenital heart disease.

Privacy and Confidentiality Provisions

Privacy Provisions

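### Aim 2 tests raw SVC saturation without reference to arterial saturation, and with HLHS and d-TGA pooled a between-patient comparison can pick up diagnosis mix

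*Combined protocol and SAP*

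**What the plan says.** Specific Aim 2 (Study Objectives) hypothesises that "PLOC will be associated with significant decreases in both oxygen consumption and SVC saturations" for at least 10 minutes before arrest. The SVC variable is the saturation itself.

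Three other places read that saturation against the arterial value:

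- Background, The Importance of Oxygen Delivery, describes a high extraction ratio as "low superior vena cava oxyhemoglobin saturations relative to arterial saturations".
- Background, SVC oxyhemoglobin saturations: "The SVC saturation is used to calculate the oxygen extraction ratio". The same sentence then gives a general guide value for compromised delivery of 40-50%.
- Potential Direct Benefits says, for any anatomy, that the saturation difference between a patient's "systemic arterial and venous circulations represents the adequacy of end organ oxygen delivery".

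No aim, outcome or analysis uses the extraction ratio or the arterial-venous difference. Appendix 1 lists cardiac output and Qp/Qs as collected, but no analysis is given for them.

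The Data Analysis Plan splits patients by PLOC and pools the two diagnoses; it mentions no diagnosis term. Its one written case-control comparison concerns VO2: 120 minutes before the event in cases against a random 120 minutes in controls, by GEE. No analysis of SVC saturation is written. The sample size section expects 3 events from 20 S1P patients and counts none from d-TGA.

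**The concern.** SVC saturation equals arterial saturation times one minus the extraction ratio. It therefore differs between patients whose arterial saturations differ, even when they extract the same share of the oxygen delivered. The Background describes HLHS as one ventricle feeding both circulations in parallel. After an arterial switch the circulations are in series, so higher arterial saturations can be expected in the d-TGA group.

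If cases are mostly HLHS and more than half the controls are d-TGA, raw SVC saturation can be lower in cases before any circulatory deterioration. Should the VO2 comparison be carried over to SVC saturation, Aim 2 could report an association with PLOC that partly reflects which operation the infant had. Separately, a fall within one infant would not show whether arterial saturation fell, flow fell or extraction rose.

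**Working it through.** **Plan's own figure.** There is none to reproduce. The documents give no mean, SD or target difference for SVC saturation, arterial saturation or their difference; the sample size calculation concerns VO2 only.

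**Inputs from the documents.** 20 HLHS and 20 d-TGA infants (Study Design); 3 events expected among 20 S1P patients (Power Calculations and Sample Size); PLOC in about 10-15% after S1P (Background), with no rate given for d-TGA.

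**Assumptions, not in the documents.** Postoperative arterial saturation 75-85% in HLHS and 95-98% in d-TGA; extraction ratio 30% in both; all 3 events in HLHS; control windows taken after surgery.

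**Step 1: gap between diagnoses.** SVC saturation = arterial saturation x (1 - extraction ratio).
- Smallest gap: (95 - 85) x 0.70 = 7.0 points.
- Largest gap: (98 - 75) x 0.70 = 16.1 points.

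**Step 2: shift from case mix.** Cases are 3 HLHS; controls are 17 HLHS + 20 d-TGA = 37. Shift = gap x 20/37.
- 7.0 x 20/37 = 3.8 points.
- 16.1 x 20/37 = 8.7 points.

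**Step 3: d-TGA events.** With k d-TGA events added to the 3 HLHS events, the multiplier is (20 - k)/(37 - k) - k/(3 + k).
- k = 1: 19/36 - 1/4 = 0.278, shift 1.9-4.5 points.
- k = 2: 18/35 - 2/5 = 0.114, shift 0.8-1.8 points.
- k = 3: 17/34 - 3/6 = 0, no shift.

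**Step 4: a different constant.** If the diagnoses share the arterial-venous difference instead of the ratio, the SVC gap equals the arterial gap, 10 to 23 points. Times 20/37, that is 5.4-12.4 points.

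**Step 5: effect on a test.** A simulation of 20,000 replicates used a t-test on one value per patient (not the GEE), a diagnosis gap in SVC saturation of 10-20 points and a within-diagnosis SD of 6-12 points. With all 3 events in HLHS, a pooled two-sided 5% test rejected about 9-20% of the time with no true case effect; the same test within HLHS rejected about 5%. With one d-TGA event added (gap 10 or 20, SD 6 or 10), the pooled test rejected 1.7-5.1%. The inflation thus depends on events being confined to HLHS.

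**Step 6: does referencing remove the gap?** Only under the matching assumption.
- Shared 24-point difference: ratio 24/80 = 0.300 in HLHS and 24/98 = 0.245 in d-TGA. Case mix moves the ratio by 0.055 x 20/37 = 0.03.
- Shared 30% ratio: difference 0.30 x 80 = 24.0 and 0.30 x 98 = 29.4 points. Case mix moves the difference by 5.4 x 20/37 = 2.9 points, smaller in cases.

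A diagnosis term is needed whichever variable is used.

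**Step 7: one infant, one SVC value, two causes.** Start at arterial 80%, SVC 56% (difference 24, ratio 0.30), with VO2 and hemoglobin constant.
- Arterial saturation falls to 70%, flow unchanged: SVC 70 - 24 = 46%; ratio 24/70 = 0.34; delivery down 10/80 = 12.5%.
- Flow falls, arterial saturation stays at 80%, SVC again 46%: difference 34; ratio 34/80 = 0.425; flow and delivery down 1 - 24/34 = 29%.

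Raw SVC saturation is identical in the two cases; the ratio is not.

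**The case against.** Much of the opposing case stands.

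- **No SVC analysis is written, and Aim 2 speaks of a change before the event.** A fixed gap between diagnoses cancels in a within-patient change. The shift in Steps 2 and 3 belongs only to a between-patient comparison of means, which the plan specifies for VO2 and leaves open for SVC saturation. The right word is can, not will.
- **A reader might infer that arterial desaturation is a false delivery signal.** The Background defines delivery as oxygen content times flow, so desaturation at unchanged flow is a true fall in delivery: 12.5% in Step 7, where the arterial-venous difference does not move at all. The defect is that raw SVC saturation does not identify the cause.
- **A reader might infer that Aim 3 has the same flaw, since its hypothesis is that continuous VO2 and "SVC saturations will add significantly to our ability to predict which patients will undergo PLOC".** The documents do not support this. Aim 3 adds the oxygen-based measurements "to standardly measured parameters (i.e. vital signs, near-infrared spectroscopy" and others, and the vital signs contain arterial saturation: "These data will include heart rate, arterial blood pressures, respiratory rate, pulse oximetry, atrial pressures, and central venous pressure". A linear predictor holding pulse oximetry and SVC saturation already spans their difference; a check on simulated data gave the same log-likelihood, -184.77, for either coding.
- **The protocol also supports the raw value.** It gives the 40-50% guide and names central venous desaturation as a consequence of inadequate delivery. This argues against replacing raw SVC saturation, but not against adding a referenced variable.
- **The stakes are limited.** The central hypothesis, the written comparison and the sample size all concern VO2.

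**Conclusion.** The point holds for the SVC half of Aim 2. The variable is not referenced to arterial saturation, although the protocol interprets it that way, and the pooled plan has no diagnosis term while expecting its events in one diagnosis. A between-patient comparison of raw SVC saturation can then be about 3.8-8.7 points lower in cases through arterial saturation and case mix alone. That size rests on assumed saturations, equal 30% extraction and all 3 events in HLHS; it reaches zero with three added d-TGA events. It does not apply to a within-patient change. The second limitation, that raw SVC saturation cannot separate desaturation from low flow or raised extraction, needs none of the case-mix assumptions.

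**What to change.** In Specific Aim 2 and the Data Analysis Plan:

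1. Pre-specify the extraction ratio, (SpO2 - SVC saturation)/SpO2, where SpO2 is the pulse oximetry saturation. Report it alongside raw SVC saturation, not in its place, with the arterial-venous difference as a sensitivity analysis.
2. Compute it from the time-aligned traces. SVC saturation is recorded every second and pulse oximetry every 5 seconds, and the protocol already commits to synchronising time stamps.
3. Analyse each variable as a within-patient change, for example the last 10 minutes against the earlier part of the same 120-minute window.
4. In any between-patient comparison, include diagnosis as a stratum or covariate, or restrict to HLHS.

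The cost is plan wording and one derived variable, with no new measurement. Some seconds will be lost where pulse oximetry drops out. Arterial blood gases are drawn at the treating team's discretion, so they cannot be relied on to fill a short pre-event window. If all events are HLHS, the d-TGA infants form a stratum without cases and the stratified comparison is in effect 3 against 17; the plan should say so.
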